### **Overview and Design of Study 1 (e.g., Aim 1, Hypotheses 1 and 2).**

Study 1 is designed to test the hypothesis that a high THC strain of marijuana will be associated with greater blood levels of THC and greater harmful effects, as compared to a lower THC strain, when used in a

naturalistic environment. To that end, regular flower marijuana users, who, according to our preliminary data, typically use marijuana with a THC potency of ~18%, will be assigned to use one of three strains with no CBD but with different THC potencies (low, medium, or high: e.g. 6%, 12%, or 18% THC for smoked flower) and regular edible marijuana users who typically purchase 10 mg products will be allowed to use as they normally would (producing naturally occurring low, medium, and high groups: e.g. less than 2.5mg to greater than 10 mg THC n=33 per group) for five days prior to participating in the experimental session. Measures will be collected at Appointment 1: (Baseline/**Session 1**), after 5 days of using the assigned strain, but in a sober condition before use in our mobile laboratory at Appointment 2: (**Session 2**), they will then return to their home to use the assigned strain and return to the mobile laboratory (**Session 3**), and 60 minutes after their last use at home (**Session 4**). Details regarding sample ascertainment, marijuana administration, timing of measures to be collected, power analyses, and the analytic plan for Study 1 follow. Thus, Study 1 will involve a 3 Cannabis strains: high, medium, and low THC x 4 (Time: 1, 2, 3, 4) mixed factorial design.

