### **Participant Recruitment and Selection.**

Recruitment to date has primarily come from flyers, business cards, and announcements placed in dispensaries in Boulder. With our new approach that involves driving the mobile lab to the participants' location, we will be able to broaden our catchment area. Interested participants will be asked to call the lab. The study technician will then screen the participant according to the inclusion criteria below. If the participant meets inclusion criteria, he or she will be scheduled for the next available appointment to complete informed consent and baseline measures. Participants will be instructed not to drink alcohol within 24 hours of the appointment, or consume caffeine for one hour prior to the appointment (note: individuals who smoke tobacco daily, consume alcohol more than 2x per week (and 3 or more drinks per occasion), or use other illicit or prescription drugs are excluded). It is important to note that dispensaries in Boulder attract customers who are diverse in age, sociodemographic status, gender, and race. In addition, we exclude University of Colorado students and employees for legal reasons, which has the added benefit of resulting in a more diverse sample. Thus, men and women of all ethnic backgrounds will be recruited into the study. We expect that the sample will reflect the diversity of Boulder/Denver area of Boulder, such that approximately 35% of the final sample will represent Latino and non-Caucasian individuals.

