### **Marijuana Administration at Home.**

Unlike other studies done in the United States to date, the proposed work will utilize a design that is observational but contains some experimental elements. Specifically, at the end of Appointment 1 (Baseline/Session 1) participants will be given instructions to purchase 3 grams of either a normally high THC strain, a medium THC strain, or a low THC strain at a dispensary (The Farm) in Boulder, Colorado. The normally high THC smoked flower strain contains 18% THC and 0% CBD and edibles can range from a low of 2.5 mg to greater than 10 mg of THC and 0 mg of CBD. **Please note the term “high” is relative given that the average potency in Colorado exceeds 18% and edibles are normally packaged in 10 mg THC doses.** The medium flower strain contains 12% THC and 0% CBD. The low flower THC strain contains 6% THC and 0% CBD. Colorado requires all strains of flower and edibles to be tested by a state licensed lab, which allows us to have a precise measure of potency to operationalize our high, medium, and low THC strains. Furthermore, the dispensary that we will work with (The Farm - see letter of support) performs cannabinoid and terpene potency testing on each batch produced. The dispensary will set aside a specific lot of the strains which will be labeled as “Strain A”, “Strain B”, and “Strain C” such that participants, dispensary staff, and research staff will be blind to which strain was purchased. Thus, 3 grams of each marijuana strain will be packaged in childproof bottles labeled as “Strain A”, “Strain B”, and “Strain C.” Our preliminary data suggests that 3 grams is sufficient for the study. [name] (co-investigator) will maintain the blind. The instruction to purchase “A” or

“B” or “C” will be urn randomized across participants such that equal numbers of male and female participants are included in the high, medium, and low conditions. The observational aspect of the design involves the instruction that participants can use as little or as much of the marijuana as they wish during the five days prior to the experimental appointment. The five-day period allows each participant to become accustomed to the strain. Subjects are prompted by email or text message to report how much was used each day using an online reporting system. On the fifth day, the research assistant calls the participant one hour prior to their appointment to remind the participant about the upcoming appointment from the research team.

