**Criteria for inclusion in the study are:**

1. Must be between the ages of 21 and 70 and provide informed consent;
2. Must have prior experience with edibles in order to be eligible to participate in the edible group;
3. Must have used marijuana at least 4x per month in the past month. This includes any form of marijuana consumption including flower, oil, wax, tinctures and edibles;

4. Must not report currently using a strain with greater than 1% CBD or less than 18% THC. This will ensure that there are no subjects who could be harmed by switching to a lower CBD/higher THC strain. All of the subjects in our preliminary study would have met this criterion.
5. Must not be a University of Colorado student or employee;
6. Must report not using other drugs (cocaine, opiates, methamphetamine) in the past 60 days or test positive on a urine test for those drugs of abuse at baseline;
7. Must not smoke greater than 5 cigarettes a day;
8. Must have a breath alcohol level of 0 at screening (to sign consent form) and must not report drinking greater than 3x per week and greater than 5 drinks on occasion for men and 4 drinks on occasion for women;
9. Female subjects must not be pregnant, as indicated by a pregnancy test which will be administered at baseline, or trying to become pregnant;
10. Must not donate plasma, blood, or platelets for 7 days prior to the 2 appointments and 7 days after;
11. Must not be in treatment for psychotic disorder, bipolar disorder or schizophrenia.

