### **Psychological Risks and Discomforts.**

While participants are experienced cannabis users to be in the study, it is still possible that some participants might experience some adverse effects from the cannabis such as increased anxiety, sleepiness, paranoia, and increased heart rate. There is a slight risk that the ingestion of cannabis may be associated with a psychotic episode.

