### **Psychological Risks and Discomforts.**

In the unlikely event that a highly experienced cannabis user has an adverse reaction to any cannabis they use and needs assistance, the research assistant will immediately notify [name] who will make himself immediately available to evaluate the condition of the participant and intervene if necessary. [name] and [name] will be on call/reachable during all scheduled appointments.

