## **XIX. PROVISIONS TO MONITOR THE DATA FOR THE SAFETY OF PARTICIPANTS**

The project manager will monitor and report to the PI on adherence to the protocol. He/she will assess adherence via periodic observation of the appointments, visual inspection of the completeness of data collection, and verification of follow-up information collected from participants (to ensure they have agreed to be contacted). He/she will give bi-weekly reports to the PI.

The project manager will use the Reportable Event eForm and/or the Deviation eForm in eRA to report all adverse events consistent with those listed under points 19.1 (adverse events) and 19.2 (deviations) in the CUB IRB policy procedures document: ([http://www.colorado.edu/VCResearch/integrity/humanresearch/SOP\\_TOC.html](http://www.colorado.edu/VCResearch/integrity/humanresearch/SOP_TOC.html)). Consistent with IRB policy, the reporting will occur:

Immediately (within 24 hours) upon learning of a study-related death, study personnel will notify the IRB via e-mail by providing a brief summary of the event. Then, within ten business days, the PI or designee will submit a Reportable Event in eRA.

(2) For any other problem or event requiring reporting to the IRB, the PI or designee will submit to the IRB a Reportable Event or Deviation in eRA as soon as possible, but no later than 10 working days from notification of event.

The PI will be in daily contact with the research assistants running the study and will be informed immediately of any adverse event.

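### Criterion 11 excludes psychotic disorder, bipolar disorder and schizophrenia only in people under treatment, so a regular user with a current but untreated diagnosis is eligible as written (low severity, participant safety only)

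*Protocol*

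**What the plan says.** Section VI of the protocol lists 11 eligibility criteria. The last reads: "Must not be in treatment for psychotic disorder, bipolar disorder or schizophrenia". No reason is given for it, and none of the other ten mentions these disorders.

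Two other places bear on who gets in. Under Participant Recruitment and Selection, a parenthetical note says that people who smoke tobacco daily, drink above a stated level, "or use other illicit or prescription drugs are excluded". The same section has the technician screen callers against the listed criteria, and section XII describes that phone interview without showing its questions.

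On risk, section XVI (Psychological Risks and Discomforts) states: "There is a slight risk that the ingestion of cannabis may be associated with a psychotic episode".

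The protocol also contains safeguards:

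- Criterion 4 bars people who report using a strain below 18% THC or above 1% CBD, with the reason: "This will ensure that there are no subjects who could be harmed by switching to a lower CBD/higher THC strain".
- For edibles, the design overview says that "regular edible marijuana users who typically purchase 10 mg products will be allowed to use as they normally would".
- During the five days at home, "Subjects are prompted by email or text message to report how much was used each day using an online reporting system".
- Section XIX states: "The PI will be in daily contact with the research assistants running the study and will be informed immediately of any adverse event".
- Section XVII names staff who "will be on call/reachable during all scheduled appointments".

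**The concern.** A rule that turns on treatment sorts people by whether they receive care, not by whether they have the condition. Of two regular users with the same diagnosis, the one under care is turned away and the one without care is admitted. The protocol gives no reason for drawing the line there.

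What is at stake is the safety of a possibly small number of participants. The study tells participants to buy 3 g of cannabis and to use it at home before Session 3, so their use during the study is not wholly spontaneous. The protocol also recognises a psychotic episode as a possible, if slight, consequence of cannabis use.

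**Working it through.** No calculation applies, because the point depends on no alpha, power, effect size or rate. The check is to read criterion 11 literally and then look for any other text that would exclude an untreated person with a current diagnosis.

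**Test case.** A person has a current diagnosis of schizophrenia, takes no medication, sees no clinician, uses cannabis regularly and meets criteria 1 to 10.

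1. *Criterion 11.* The person is not in treatment, so the condition is met and the person is eligible.
2. *Criteria 1 to 10.* These cover age and consent, experience with edibles, frequency of use, strain potency, university affiliation, other drugs, cigarettes, alcohol, pregnancy and blood donation. None concerns a psychiatric diagnosis.
3. *Prescription-drug note in the recruitment section.* It excludes people who take prescription drugs. The test case takes none. This filter works on the same side as criterion 11: it catches medicated people and leaves unmedicated ones.
4. *Session 1 measures in section XII.* The urine screen is for illicit drugs. The BDI-II and BAI cover depression and anxiety, and their stated use is to examine comorbidity and adjust for baseline differences, not to decide entry. The POMS records mood. No listed measure is described as covering psychotic or bipolar disorder.
5. *Withdrawal (section XV).* The grounds given for removing an individual without consent are failure to follow instructions and abusive behaviour. Neither is psychiatric.

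Nothing shown excludes the test case.

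**How much exposure the study could add.** For flower, usual potency is at least 18% THC by criterion 4, and the assigned levels are 6%, 12% and 18%. Against the 18% floor the differences are 6 − 18 = −12, 12 − 18 = −6 and 18 − 18 = 0 percentage points, so assigned potency is at or below usual potency in every arm. Potency is not dose: the amount taken is left to the participant and could go up or down. Edible users keep their usual pattern. The document supports limited added exposure, but gives no figure for it.

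**What the safeguards do.** The daily prompt is described as asking about the amount used; no symptom question is mentioned. The on-call statement covers scheduled appointments, whereas most of the use takes place at home over five days. Immediate notice to the lead investigator follows an adverse event. All of these act after enrolment, and none identifies the test case before entry.

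**The case against.** The strongest reply is that nothing here is misstated or contradicted. Criterion 11 is clear and can be asked as one question. Entrants already use cannabis regularly, flower potency is matched or lowered, edible users carry on as usual, and the slight risk in section XVI is attributed to taking cannabis, which these people already do. The study also deliberately favours external validity, and tighter entry works against that. Most of this stands, and it is why the point is minor. It does not explain why a treated person is excluded and an untreated person with the same diagnosis is not.

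A reader might infer more than the text supports:

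- *That criterion 11 was written to guard against psychotic episodes and fails at that purpose.* The protocol states no purpose for it, and the risk section does not refer to it. The gap can be described without assigning a purpose.
- *That untreated people will in fact be enrolled.* The phone-screen questions are not shown, and staff may ask more than the criterion requires. The point concerns the written rule only.
- *That the protocol must exclude any lifetime diagnosis or past episode.* That would remove long-remitted users from a study that puts external validity first. The document offers no evidence on where to draw that line.
- *That the share of criteria or measures covering these disorders shows how large the problem is.* One well-worded criterion would be enough, and most Session 1 measures were never meant as eligibility screens.

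**Conclusion.** The point holds in a limited form. As written, criterion 11 admits a regular user with a current but untreated diagnosis of one of the three disorders, and no other text shown in the protocol closes the gap.

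Severity is low. It is a matter of participant safety alone; the estimand, the analysis and the planned sample (99 analysed, about 111 recruited) are untouched. The number of people concerned and any rise in their risk cannot be derived, and neither is claimed.

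The conclusion assumes that eligibility is decided on the criteria as printed, and that participants report their usual strain accurately for criterion 4. If the phone screen already asks about diagnosis regardless of treatment, the gap is one of wording only, and the rewording would simply record existing practice.

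**What to change.** Replace the treatment condition in criterion 11 with a diagnosis condition, for example: *Must have no diagnosis of schizophrenia, bipolar disorder or a psychotic disorder, whether or not in treatment.* This keeps the three conditions already chosen. Ask about it by self-report at the existing phone screen and again at Appointment 1, before the instruction to purchase is given.

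The investigator should decide, and state in the criterion, whether a remitted disorder or a past psychotic episode also excludes. Either choice is defensible.

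The cost is one reworded line and a self-report question at two contacts that already take place. Expect a few more screen failures and a slightly narrower sample. The number to recruit stays the same, although a few more people may need to be screened to reach it. Self-report will still miss people whose disorder has never been diagnosed.

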## **VII. VULNERABLE POPULATIONS**

---

This study does not include any vulnerable populations.

## **VIII. RECRUITMENT METHODS**

---

Subjects will be recruited from the front range area through the social media sites (e.g., facebook, twitter, etc.) or websites of cannabis dispensaries or patient advocacy groups. All of these advertisements will describe the opportunity to contribute to research regarding cannabis use. Specifically, the posts on social media will include the following wording “The University of Colorado is conducting research on how levels of CBD and THC are related to mood and cognition.” All social media pages will provide additional information about the study (see attached word file). The wording used on the social media page may also be used in flyers or other advertisements, or directly mailed to potential participants. We request specify age groups by zip code through a direct marketing company and they provide names and addresses.

## **IX. COMPENSATION**

---

Participants will receive \$150 at the end of the study. If a participant does not complete the study, payment will be pro-rated at \$50 for Appointment 1 and at Appointment 2: \$50 for session 2, and \$25 for Session 3 and 4. Given the amount of time required in the study and the travel to and from the lab for Appointment 1, this is a reasonable amount of money to compensate participants for their time and effort. Thus, there is no question of coercion.

## **X. CONSENT PROCESS**

---

When a participant arrives for his or her first appointment at the Center for Innovation and Creativity (CINC), a member of the research team will greet him or her in the first-floor lobby. The research assistant will take the participant to a private room and provide the participant with a copy of the informed consent document. Prior to asking the participant to sign the consent form, the trained research assistant and the participant will

have a discussion regarding the research study. Additionally, the research assistant will be available to answer any questions he or she may have about the study. Participation will be clearly stated as voluntary, with the option to withdraw at any time. There will be no deception involved with this study. After discussing the study and going over the consent form with the researcher, the participant will initial and sign the informed consent document.

## **XI. PROCESS TO DOCUMENT CONSENT IN WRITING**

---

In accordance with 45 CFR 46.117, an unsigned copy of the form used to document consent will also be given to the study participant.

## **XII. PROCEDURES**

---

Participants will contact the researchers with their interest by phone or by e-mail. The researcher will respond with an overview of the study and answer any questions the potential participant has before screening the caller for preliminary eligibility. In the case that a potential participant requests more information via e-mail, the research assistant responding to the e-mail will ask the participant to call the lab phone number (same phone number provided on all study advertisements) for more information, or e-mail the study team a phone number at which the potential participant could be reached and a desirable time for the research staff to call. This process will help to ensure participants have ample opportunity to be informed of the main study components, ask questions, and decide if they are willing to participate before they sign up for the study. If the participants meet the study criteria during the initial phone interview, they will be invited to come to the CINC for the Appointment 1, baseline session.

**Appointment 1, Baseline Assessment Procedure (Session 1).** Subjects who meet inclusion criteria will be scheduled for the first available appointment, baseline session. After arriving at the lab, subjects will be provided with a consent form. Each subject will be breathalyzed to insure that they have not been drinking alcohol prior to each appointment. A urine toxicology screen will also be administered to insure that subjects have not recently use illicit drugs other than cannabis. Additionally, female participants will be required to take a urine pregnancy test (provided by the study team at no cost to the participant). A member of our research team who has completed a certified training in phlebotomy will collect a blood sample. All blood draw procedures performed during this study will involve collecting venous blood via venipuncture of a peripheral arm vein using standard, sterile phlebotomy techniques. Subjects will then complete measures related to alcohol and drug use, cannabis withdrawal, cannabis craving, measures of mood, and neurocognitive measures (see section below for details of measures to be completed). After completing the measures, each participant will be scheduled for their 2nd appointment to include Sessions 2, 3, & 4. Before the participant leaves this appointment they will be given instructions to purchase 3 grams of either a normally high THC strain, a medium THC strain, or a low THC strain at a dispensary (The Farm) in Boulder, Colorado to be used for 5 days as they normally would, they will also be given a gut microbiome collection kit to take home with them and bring back at their 2nd appointment.

**Appointment 2, Mobile Lab Experimental Procedure (Session 2, 3, 4).** For Sessions 2, 3 & 4 the study coordinator will drive the mobile lab to a location close to the participant's home. The participant will come to the mobile lab where they will complete a blood draw (22 ml), self-report measures, and the cognitive tests for Session 2. At the end of Session 2, participants will return to their home to use the assigned strain as they normally would.

Then they will return to the mobile laboratory for Session 3, where a blood draw self-report measures, and the cognitive battery will be collected in the mobile lab. The blood draw (22 ml), questionnaires and cognitive battery will be repeated at 1 hour after Session 3 at the mobile lab (Session 4). After the last assessment, the participant will be paid \$150 to compensate them for their time and effort (Appointment 1: \$50 for Session 1, Appointment 2: \$50 for Session 2, \$25 for Session 3, \$25 for Session 4), debriefed, and escorted back to their home.

Name of instrument/tool/procedure	Purpose (i.e. what data is being collected?)	Time to Complete
Appointment 1: Baseline/Session 1		
Urine Testing	
 
A urine sample will test for illicit drugs other than marijuana (e.g. cocaine, benzodiazepines, opiates, MDMA, sedatives, or methamphetamine).
 
	
Pregnancy Screening	
 
All female participants will take a urine pregnancy test.
 
	
Demographics Questionnaire	
 
Age, sex, marital status, race/ethnicity, SES, occupation, income, education, and religious affiliation.
 
	
Alcohol Use History Questionnaire	
 
Targets the frequency of lifetime and recent use for alcohol.
 
	
Pain Intensity	
 
Consists of one item asking about the participant's level of pain in the past seven days. Participants are asked to rate their pain on a scale from 0 (no pain) to 10 (worst imaginable pain).
 
	
Promis Pain Interference CAT	
 
This asks participants about how their experience of pain interfered with or affected their enjoyment of various daily activities in the past seven days. The scale is computer-adapted and has a minimum of four questions and a maximum of 12 questions. The questions ask for a response on a 5-point scale. Some of the items are rated: Not at all; A little bit; Somewhat; Quite a bit; Very much; other items are rated: Never; Rarely; Sometimes; Often; Always.
 
	
Health Related Quality of Life	
 
This is a Short Form 36 Health Survey, which consists of 36 questions across nine health domains and is sensitive in detecting changes over time in health-related quality of life.
 
	

Self-Rated Question of Diet Quality	
 
In general, how healthy is your overall diet? Would you say (1) excellent, (2) very good, (3) good, (4) fair, or (5) poor? (Loftfield, Yi, Immerwahr, Eisenhower)
 
	
Leisure-Time Categorical Item (L-Cat)	
 
A single item comprised of six descriptive categories ranging from inactive to very active (Kiernan, Schoffman, Lee, Brown, Fair, Perri, & Haskell, 2013). Each category consists of 1–2 sentences describing common activity patterns differing in frequency, intensity, duration, and types of activities, thus encompassing content validity (van Poppel, Chinapaw, Mokkink, van Mechelen, & Terwee, 2010).
 
	
Marijuana Consumption Questionnaire (MCQ)	
 
Ask participants to reflect on the frequency and quantity of their cannabis use, age of first use, and perceived availability of cannabis. (Heishman, Singleton, & Liguori, 2001)
 
	
Marijuana Dependence Scale (MDS)	
 
The MDS based on DSM V criteria that were converted to a self-report measure. Individuals respond 'yes' or 'no' to each dependence item (e.g., "When I smoked marijuana, I often smoked more or for longer periods of time than I intended"). The items are then summed to form the scale. This scale has been previously used in the cannabis literature. The internal consistency of the MDS (based on the DSM IV) was good in our pilot study (<math>\alpha = .73</math>) and even better in previously published reports (<math>\alpha = .85</math>; see Stephens, Roffman, & Curtin, 2000).
 
	
Alcohol Use Disorders Identification Test (AUDIT)	
 
The AUDIT (Babor et al., 2001) will be used to examine the extent of co-morbid alcohol use and problems related to alcohol use.
 
	
The Beck Depression Inventory-II (BD-II)	
 
Consists of 21 scaled statements designed to assess symptoms of depression and will be administered to examine comorbid depression and covary baseline differences if necessary. (Beck, Steer, Ball, & Ranieri, 1996)
 
	
The Beck Anxiety Inventory (BAI)	
 
Consists of 21 items, each describing a common symptom of anxiety and will be administered to examine comorbid anxiety and covary baseline differences if necessary. (BAI; Beck, Epstein, Brown, & Steer, 1988)
 
	

Marijuana Withdrawal Checklist (MWC)	
 
• A 15-item scale used to collect information on withdrawal symptoms that one may have experienced the last time they stopped smoking marijuana. (Budney et al., 2003)
 
	
Physical Activity Participation	
 
• This is one question that asks participants to list 3 sports/activities they engage in. (Bryan, A.D., & Rocheleau, C.A. (2002)
 
	
Brief Sensation Seeking Scale (BSSS)	
 
• The BSSS will be used to examine whether sensation seeking moderates the effect of cannabis consumption on exercise cognitions. (Hoyle, Stephenson, Palmgreen, Lorch, & Donohew, 2002)
 
	
Expectancy Questions	
 
• These 3 questions assess a participant’s knowledge of cannabis and their health
 
	
The Pittsburgh Sleep Quality Index (PSQI)	
 
• The Pittsburgh Sleep Quality Index (PSQI) is an effective instrument used to measure the quality and patterns of sleep. It differentiates “poor” from “good” sleep by measuring seven domains: subjective sleep quality, sleep latency, sleep duration, habitual sleep efficiency, sleep disturbances, use of sleep medication, and daytime dysfunction over the last month. The client self rates each of these seven areas of sleep
 
	
Session 1 & 2		
Timeline Follow-Back (TLFB)	
 
• TLFB is used to assess daily substance use for 30 days prior to the baseline session. Our modified TLFB procedure will estimate both frequency of marijuana use and amount used per day, using visual stimuli as well as the method of administration. (Sobell & Sobell, 1992) (Sobell, Sobell, & VanderSpek, 1979)
 
	
Session 2		

The Pittsburgh Sleep Quality Index (PSQI)	
 
The Pittsburgh Sleep Quality Index (PSQI) is an effective instrument used to measure the quality and patterns of sleep. It differentiates “poor” from “good” sleep by measuring seven domains: subjective sleep quality, sleep latency, sleep duration, habitual sleep efficiency, sleep disturbances, use of sleep medication, and daytime dysfunction over the last month. The client self rates each of these seven areas of sleep
 
	
Cold Presser Task	
 
Participants immerse their hand in cold liquid and withdraw their hand from the liquid (pain tolerance) and the timing is recorded. There is a risk of discomfort.
 
	
Session 2 & 3		
Exercise Cognitions	
 
This measure will be used to examine the acute cognitive effects of cannabis consumption on participants’ exercise cognitions, specifically exercise intentions, motivation, and self-efficacy. These measures are slight variations of assessments of exercise cognitions used in our prior work (Bryan & Rocheleau, 2002).
 
	
Session 3 & 4		
The Drugs Effects Questionnaire (DEQ)	
 
The Drug Effects Questionnaire (DEQ) is a 5 items visual analog scale used to measure the strength of marijuana as well as the desirable effects (de Wit & Phillips, 2012).
 
	
The Addiction Research Center Inventory	
 
The Addiction Research Center Inventory (ARCI; Martin, Sloan, Sapira, & Jasinski, 1971), including the ARCI—Marijuana (M) scale (Chait, Fischman, & Schuster, 1985) will be used to measure subjective effects of marijuana in addition to drug-induced euphoria, stimulant-like effects, intellectual efficiency and energy, sedation, dysphoria, and other somatic effects.
 
	
Session 4		
Cold Presser Task		

 
Participants immerse their hand in
 
		

cold liquid and withdraw their hand from the liquid (pain tolerance) and the timing is recorded. There is a risk of discomfort.		
Assessment of Blind and Potency of Marijuana	
 
At the end of the experimental session, participants will be asked to guess which strain they received and to guess the potency of THC and CBD in that strain.
 
	
Sessions 1, 2, 3, 4		
Venous Blood Draw	
 
A BD Vacutainer Safety-Lok needle and microtainer will be used to obtain blood through a peripheral intravenous line (PIV).
 
	
Heart Rate	
 
Heart rate will be collected using a basic fingertip pulse oximeter.
 
	
Neurocognitive Battery	
 
The cognitive battery will include the Flanker Inhibitory Control and Attention task, the Dimensional Change Card Sort Task, the Picture Sequence Memory Test, the Auditory Verbal Learning Test (Rey), and the List Sorting Working Memory Test. The battery covers the domains found to be sensitive to the effects of marijuana (for review see Ranganathan & D'Souza, 2006).
 
	
Marijuana Craving Questionnaire (MCQ)	
 
A Marijuana Craving Questionnaire will be used to assess craving at each time point during the experimental session. The MCQ was adapted from a valid tobacco craving questionnaire (Tiffany & Drobes, 1991) and has proven to be useful in cannabis studies (Budney et al., 2003). In our pilot study, internal consistency was very high (<math>\alpha = .90</math>).
 
	
Profile of Mood States (POMS)	
 
The Profile of Mood States (POMS) will be used to collect baseline information on mood as well as information on mood changes throughout the study. (Johanson & Uhlenhuth, 1980; McNair, Lorr, & Droppelman, 1971)
 
	
Appointments 1 & 2:		
	Procedures/Tools	Time to complete
Appointment 1 Baseline/Session 1	Informed consent & study orientation; BAC test; Urine drug test; Pregnancy test; Blood draw; Heart rate; Questionnaires; Cognitive battery; Appointment 2 scheduling	2.5hours

Appointment 2 Session 2	Heart rate; Questionnaires; Cognitive battery; Blood draw.	1 hours
Session 3	Heart rate; Questionnaires; Cognitive battery; Blood draw; 1 hour relaxation	1 hours
Session 4	Heart rate; Questionnaires; Cognitive battery; Blood draw; Debriefing; Monetary Compensation	1 hour
TOTAL TIME		5.5hours

